10.3.4 Removal of Patients from the Study

Patients will be informed that they are free to withdraw from the study at any time. If necessary, the Investigator may withdraw a patient from the study to protect the health of that patient. The clinical report will include all reasons for early withdrawals.

CONFIDENTIAL PROTOCOL

A Randomized, Double-Blind, Vehicle-Controlled, Parallel-Design, Multiple-Site Clinical Study to Evaluate the Therapeutic Equivalence of Ketoconazole Cream 2% (Encube Ethicals Pvt Ltd) to Ketoconazole Cream 2% (G&W Laboratories Inc.) in the Treatment of Tinea Pedis

Reasons for removal may include the following:

- Patient withdrew consent.
- Significant AE that led the Investigator or patient to withdraw for safety reasons.
- Non-compliance with protocol requirements (e.g., use of restricted medication, not following dosing procedures, failure to make scheduled study visits in a timely fashion).
- Pregnancy
- Negative baseline culture results
- Development of an intercurrent condition or complication that could affect the safety of the patient or the validity of evaluation of the patient's clinical state to an extent considered significant by the Investigator
- Significant worsening of tinea pedis such that the Investigator and/or patient believe it is in the best interest of the patient to withdraw from the study and be provided alternative treatment.
- Patient enrolls in another clinical trial, or is found to have previously enrolled in this clinical trial.

Patients who withdraw or are removed from the study will not be replaced.

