11.3 Study Populations

11.3.1 Per-Protocol Population

The PP population will include all randomized patients who:

- Met all inclusion and exclusion criteria.
- Made the final study visit within the protocol window of Day 56 ± 4 days (Day 52 to Day 60 inclusive) with no protocol violations that would affect the treatment evaluation.
- Did not have any significant protocol deviations.
- Were compliant with dosing between 75%-125% of the required doses.
- Had a positive baseline KOH and fungal culture for *Trichophyton rubrum*, *Trichophyton mentagrophyties* or *Epidermophyton floccosum*.

Patients discontinued from the study because of lack of treatment effect after completing at least 14 days of treatment will be included in the PP population as Therapeutic Failures provided they had a positive baseline KOH, positive baseline fungal culture, and did not have any significant protocol deviations. For these patients, there will be no mycological testing at time of discontinuation; therefore, they will be considered Therapeutic Failures in the primary analysis but the Mycological Cure data will be set to missing for the secondary endpoint.

Patients who meet the criteria above, but who also used topical drug therapy for irritation or pruritus on the feet after the treatment phase of the study will be included in the PP population as Therapeutic Failures. If no mycological testing is performed, the patients will be considered Therapeutic Failures in the primary analysis but the Mycological Cure data will be set to missing for the secondary endpoint.

All analyses performed using the PP population will be done on an observed case basis (i.e., no last observation carried forward [LOCF] will be performed).

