11.8 Safety Analysis

Adverse events (AEs) will be classified using standard Medical Dictionary for Regulatory Activities (MedDRA) terminology Version 21.0 or higher and summarized by treatment group. Summary tables comparing the type, date of onset, date of resolution, incidence, severity, relationship to the study product, outcome, and action taken will be prepared by treatment group. If sufficient data exist, then AE frequencies will be compared among the three treatments using Fisher's exact test; if this test is statistically significant at the 5% significance level, then a pairwise Fisher's exact test comparing Test and Reference will be conducted.

CONFIDENTIAL PROTOCOL

A Randomized, Double-Blind, Vehicle-Controlled, Parallel-Design, Multiple-Site Clinical Study to Evaluate the Therapeutic Equivalence of Ketoconazole Cream 2% (Encube Ethicals Pvt Ltd) to Ketoconazole Cream 2% (G&W Laboratories Inc.) in the Treatment of Tinea Pedis

Signs and symptoms of tinea pedis will not be considered AEs, unless in the Investigator's opinion, they have increased in frequency and/or severity to such an extent that the Investigator/patient considers that it is in the patient's best interest to be discontinued from further participation in the study and given alternative therapy for their condition.

Concomitant medication use will be tabulated by patient.

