6. EFFICACY VARIABLES AND EFFICACY ENDPOINTS

Efficacy Variables

The primary and secondary efficacy variables are the outcome of the KOH test (negative or positive), outcome of the mycological culture (negative or positive), and signs and symptoms scores.

Primary Efficacy Endpoint:

The primary efficacy endpoint is the proportion of patients in each treatment group with a Therapeutic Cure of tinea pedis at the test-of-cure visit two weeks after the end of treatment (Day 56 ± 4).

Secondary Efficacy Endpoints:

The secondary efficacy endpoints are:

- The proportion of patients in each treatment group with a Clinical Cure at Day 56 ± 4 .
- The proportion of patients in each treatment group with a Mycological Cure at Day 56 ± 4 .

Definitions

1. **Therapeutic Cure:** To be considered a Therapeutic Cure, the patient must have both Clinical and Mycological Cure of tinea pedis.
2. **Therapeutic Failure:** A patient will be considered a Therapeutic Failure if:

NOVUM PHARMACEUTICAL RESEARCH SERVICES
STATISTICAL ANALYSIS PLAN

Ketoconazole Cream 2%

Protocol / Study No. 71875502

- a. the patient is a Clinical or Mycological Failure
- b. the patient was considered to have an insufficient therapeutic response
- c. the patient used topical drug therapy for irritation or pruritus on the feet between Visit 2 (Day 42 ± 4 days) and Visit 3 (Day 56 ± 4 days)
3. **Clinical Cure:** To be considered a clinical cure the patient's total severity score must be ≤ 2 with no individual severity score > 1 .
4. **Clinical Failure:** A patient will be considered a Clinical Failure if the patient's total severity score is > 2 or any individual score is > 1 .
5. **Mycological Cure:** To be considered a mycological cure the patient must have a negative KOH test and a negative fungal culture.
6. **Mycological Failure:** A patient will be considered a Mycological Failure if the patient's KOH test is positive or the patient's fungal culture is positive.

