Patients discontinued early for reasons other than lack of treatment effect will be excluded from the PP population and included in the mITT population using LOCF. Patients who qualify for inclusion in the mITT population with missing endpoint data who were not discontinued for lack of treatment effect will also be evaluated using LOCF; that is, if a patient who was not discontinued for lack of treatment effect does not have KOH or mycological culture results at Visit 3, this patient will be evaluated for the primary and secondary endpoints using LOCF from Visit 1. Patients who discontinued because of lack of treatment effect will not have LOCF performed.

Patients who meet the criteria above, but who also used topical drug therapy on the feet for the treatment of irritation or pruritus after the treatment phase of the study will be included in the mITT as Therapeutic Failures. If no mycological testing is performed, these patients will be considered Therapeutic Failures in the primary analysis but the Mycological Cure data will be set to missing for the secondary endpoint. No LOCF will be performed.

Safety Population

The Safety population will include all randomized patients who use at least one dose of product.

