8.1 Baseline Characteristics

8.1.1 Patient Disposition

The patient disposition information will be summarized by treatment group as well as total. The number of patients randomized will be tabulated by treatment group and total. In addition, completion status and primary reason for withdrawal will be summarized by treatment group and total.

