8.2 Efficacy Analyses

8.2.1 Efficacy Analyses on Primary and Secondary Endpoints

Therapeutic Equivalence

Therapeutic equivalence will be evaluated for the primary endpoint in the per-protocol (PP) population. If the 90% confidence interval (calculated using Yates' continuity correction) on the absolute difference between the proportion of patients with a Therapeutic Cure in the Test and Reference groups ($p_T - p_R$) is contained within the range [-20%, +20%] then therapeutic equivalence of the Test product to the Reference product will be considered to have been demonstrated.

The same statistical approach will be conducted for analyses of the secondary endpoints in the PP population.

To declare therapeutic equivalence of the Test product to the Reference product, equivalence must be demonstrated for only the primary endpoint in the PP population.

Patients who are missing mycological culture data at the test-of-cure visit will not be included in the analysis for the secondary endpoint of Mycological Cure.

Superiority to Placebo

NOVUM PHARMACEUTICAL RESEARCH SERVICES
STATISTICAL ANALYSIS PLAN

Ketoconazole Cream 2%

Protocol / Study No. 71875502

Superiority of the Test and Reference products against the Placebo product for the primary endpoint will be evaluated in the mITT population using, if necessary, LOCF as described in section 11.3.2 of the protocol.

Patients discontinued early for reasons other than lack of treatment effect will be excluded from the PP population and included in the mITT population using LOCF. Patients who qualify for inclusion in the mITT population with missing endpoint data who were not discontinued for lack of treatment effect will also be evaluated using LOCF; that is, if a patient who was not discontinued for lack of treatment effect does not have KOH or mycological culture results at Visit 3, this patient will be evaluated for the primary and secondary endpoints using LOCF from Visit 1. Patients who discontinued because of lack of treatment will not have LOCF performed.

Patients who meet the criteria above, but who also used topical drug therapy on the feet for the treatment of irritation or pruritus after the treatment phase of the study will be included in the mITT as Therapeutic Failures. If no mycological testing is performed, these patients will be considered Therapeutic Failures in the primary analysis but the Mycological Cure data will be set to missing for the secondary endpoint. No LOCF will be performed.

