9. TABLE, LISTING AND FIGURE SHELLS

The following shells provide a framework for the display of data from this study. These shells may not be reflective of every aspect of this study but are intended to show the general layout of the Tables, Listings and Figures that will be included in the final clinical study report. Tables, Listings and Figures are numbered following the ICH structure. Table headers, variables names and footnotes will be modified as needed following data analyses. All descriptive and inferential statistical analyses will be performed using SAS® statistical software Version 9.4 or higher, unless otherwise noted.

NOVUM PHARMACEUTICAL RESEARCH SERVICES
STATISTICAL ANALYSIS PLAN

Ketoconazole Cream 2%

Protocol / Study No. 71875502

TABLE, LISTING AND FIGURE SHELLS

NOVUM PHARMACEUTICAL RESEARCH SERVICES
STATISTICAL ANALYSIS PLAN

Ketoconazole Cream 2%

Protocol / Study No. 71875502

T14.1.1 Summary of Patient's Disposition

(Randomized Population)

Patients Randomized	Test	Reference	Placebo	Total
	N = xxx n (%)			
Completed Study	xxx (xx.x)	xxx (xx.x)	xxx (xx.x)	xxx (xx.x)
Terminated Early	xxx (xx.x)	xxx (xx.x)	xxx (xx.x)	xxx (xx.x)
Adverse event	xxx (xx.x)	xxx (xx.x)	xxx (xx.x)	xxx (xx.x)
Lack of efficacy	xxx (xx.x)	xxx (xx.x)	xxx (xx.x)	xxx (xx.x)
Lost to follow-up	xxx (xx.x)	xxx (xx.x)	xxx (xx.x)	xxx (xx.x)
Negative baseline culture result	xxx (xx.x)	xxx (xx.x)	xxx (xx.x)	xxx (xx.x)
Noncompliance with study drug	xxx (xx.x)	xxx (xx.x)	xxx (xx.x)	xxx (xx.x)
Patient scheduled/came in early for Visit 3				
Pregnancy	xxx (xx.x)	xxx (xx.x)	xxx (xx.x)	xxx (xx.x)
Protocol deviation	xxx (xx.x)	xxx (xx.x)	xxx (xx.x)	xxx (xx.x)
Significant worsening of condition requiring alternative or supplemental therapy	xxx (xx.x)	xxx (xx.x)	xxx (xx.x)	xxx (xx.x)
Withdrawal by subject	xxx (xx.x)	xxx (xx.x)	xxx (xx.x)	xxx (xx.x)
Other	xxx (xx.x)	xxx (xx.x)	xxx (xx.x)	xxx (xx.x)

Test: Ketoconazole Cream 2% (Encube Ethicals Pvt Ltd)

Reference: Ketoconazole Cream 2% (G&W Laboratories Inc.; Registrant: Teva Pharmaceuticals USA Inc.)

Placebo: Placebo Cream (Test vehicle) (Encube Ethicals Pvt Ltd)

N = number of patients randomized in that particular group; n = number of patients with data available for that particular group; total % is based on N

PROGRAM: L:\DEV\755\71875502\SAS\PGM\XXXX
Created on: ddmmmyy hh:mm

OUTPUT: L:\DEV\755\71875502\SAS\OUT\XXXX
Page 1 of N

NOVUM PHARMACEUTICAL RESEARCH SERVICES
STATISTICAL ANALYSIS PLAN

Ketoconazole Cream 2%

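### Does leaving lack of treatment effect undefined let a withdrawal code decide who counts as a failure in the per-protocol equivalence analysis?

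*SAP*

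**What the plan says.** Four parts of the plan bear on this.

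- **Who stays in PP.** Protocol 11.3.1 and SAP section 7 keep as Therapeutic Failures those discontinued "because of lack of treatment effect after completing at least 14 days of treatment will be included in the PP population", provided baseline KOH and culture were positive and there was no significant deviation. For everyone else SAP section 7 says: "Patients discontinued early for reasons other than lack of treatment effect will be excluded from the PP population". They go into mITT with LOCF.
- **What counts as failure.** SAP section 6, item 2b, makes a patient a Therapeutic Failure if "the patient was considered to have an insufficient therapeutic response". No criterion is attached to that phrase or to lack of treatment effect.
- **Reasons for leaving.** Protocol 10.3.4 names "Significant worsening of tinea pedis such that the Investigator and/or patient believe it is in the best interest of the patient to withdraw" and has no lack-of-effect item. SAP 8.1.1 says that "completion status and primary reason for withdrawal will be summarized by treatment group and total". The T14.1.1 shell has separate rows for adverse event, lack of efficacy, and "Significant worsening of condition requiring alternative or supplemental therapy". Protocol 11.8 allows worsening to be an adverse event when the patient is judged better served "to be discontinued from further participation in the study and given alternative therapy for their condition".
- **Where equivalence is decided.** SAP 8.2.1: "equivalence must be demonstrated for only the primary endpoint in the PP population".

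**The concern.** One clinical course, a foot that gets worse until the patient leaves, could be recorded under three labels, and the plan does not say which of them amount to lack of treatment effect. If a programmer matches the PP rule only to the lack-of-efficacy row, a patient withdrawn for worsening leaves PP. If worsening is read as a form of lack of effect, the same patient stays in as a failure. The first reading removes patients because of their outcome.

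PP is the sole basis for the equivalence decision, it is analysed on observed cases, and no sensitivity analysis is planned for it. Removing failures from one active arm raises that arm's observed cure rate. If worsening were concentrated in a poorer Test product, the two products would look more alike than they are. If it were concentrated in Reference, a sound Test product could lose power.

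**Working it through.** **The plan's own figure.** Inputs from SAP section 5: Reference cure 50%, Test 45%, 172 per active arm, limits ±20%, 90% interval with Yates' correction.

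Interval: d ± (1.645 × SE + c), where SE = √(pT(1−pT)/nT + pR(1−pR)/nR) and c = ½(1/nT + 1/nR).

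- SE = √(0.45 × 0.55/172 + 0.50 × 0.50/172) = 0.0538; c = 1/172 = 0.0058.
- Lower side: (0.15 − 0.0058)/0.0538 − 1.645 = 1.036. Upper side: (0.25 − 0.0058)/0.0538 − 1.645 = 2.895.
- Power = Φ(1.036) + Φ(2.895) − 1 = 84.8%. Exact binomial enumeration gives 85.6%. The stated figure of about 85% reproduces.

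**What the coding could do.** The documents give no worsening rate, so the rates w below are assumptions. Each active arm has 172 patients including worseners. Their number is binomial(172, w), and the cure rate among the rest is p/(1 − w), so the true rate with worseners counted as failures stays at p. The first result column puts the truth at the margin (Test 30%, Reference 50%). The second uses the planned rates (45%, 50%).

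| Handling of worseners | Assumed w, Test / Reference | False equivalence | Power |
|---|---|---|---|
| Counted as failures | any | 3.8% | 85.6% |
| Excluded | 2% / 2% | 3.2% | 83.8% |
| Excluded | 5% / 5% | 2.4% | 81.9% |
| Excluded | 3% / 1% | 4.6% | 87.7% |
| Excluded | 4% / 2% | 4.2% | 87.2% |
| Excluded | 5% / 3% | 3.9% | 86.7% |
| Excluded | 5% / 2% | 4.8% | 88.7% |
| Excluded | 2% / 0% | 4.9% | 88.2% |
| Excluded | 5% / 0% | 7.1% | 91.7% |
| Excluded | 0% / 2% | 2.5% | 80.0% |
| Excluded | 0% / 5% | 1.2% | 69.9% |

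With no worsening in Reference, the 5% level is crossed between w = 2.1% (4.98%) and w = 2.2% (5.04%) in Test. The 5% / 2% row sits close to the limit, so a wider Test excess would be expected to cross it too. Equal worsening makes exclusion conservative for type I error and costs 85.6 − 83.8 = 1.8 to 85.6 − 81.9 = 3.7 points of power.

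**A single data set near the limit.** Test 69/172 against Reference 86/172 gives −19.25% to −0.52%, which passes. Adding four Test worseners as failures (69/176 against 86/172) gives −20.09% to −1.50%, which fails. Adding four to each arm (69/176 against 86/176) gives d = −9.66%, SE = 0.0527, c = 0.0057, and a lower bound of −9.66 − 8.66 − 0.57 = −18.89%, which passes. What matters is imbalance.

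**Which reading the text supports.** In Protocol 10.3.4 worsening is the only removal reason that describes poor response to treatment. If it did not count as lack of treatment effect, the retention rule in 11.3.1 would correspond to nothing on that list. Item 2b of SAP section 6 points the same way: a patient who worsens enough to need other treatment has responded insufficiently. T14.1.1 is a disposition table for all randomized patients and assigns nobody to PP; SAP section 9 describes the shells as a general framework that may be modified. Protocol 11.8 governs when worsening is reported as an adverse event and does not make that the reason for discontinuation, so the two records can coexist.

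**mITT.** A worsener without Visit 3 mycology is carried forward from a positive Visit 1 and is a Therapeutic Failure. A lack-of-effect withdrawal is a failure without LOCF. The primary superiority endpoint is the same either way; only the secondary Mycological Cure endpoint can depend on the code.

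**The case for a change.** The strongest case for a change is that PP membership is a derived variable of the kind a SAP exists to fix, and two programmers could build different PP data sets from these pages. The list in Protocol 10.3.4 is open-ended, so the inference from it is not conclusive, and T14.1.1 does offer a lack-of-efficacy row that the retention rule could be matched to. A handful of patients can turn a borderline result, as 69/172 shows. Blinding stops anyone coding by known assignment but does not stop exclusion by outcome, and a mapping chosen after unblinding would be open to challenge.

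The textual part stands: no sentence settles the reading. The rest carries less weight. Investigators, monitors and data staff are blinded, and the statistician receives the schedule only after database lock (SAP section 4). Listing L16.2.1 shows each discontinued patient with reason and population, and L16.2.3.1 shows each PP exclusion with its reason, so any reader can reclassify the patients and recompute the interval. The SAP was prepared from the study casebook (section 1), which is not among the documents reviewed and may define the codes. Patients who leave before 14 days or with a significant deviation fail the retention conditions under either reading, so the modelled effect is an upper view. A sensitivity analysis counting withdrawals before 14 days as failures would depart from the plan's own 14-day condition and is a matter of preference.

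**Conclusion.** This is an unwritten definition that blinded analysts can be expected to fill sensibly, and no change is called for. The structure of the removal list and failure item 2b favour keeping worseners in PP as failures; under that reading power is 85.6% and false equivalence at the margin 3.8%, as planned. Under the less natural reading, equal worsening of 2% to 5% lowers false equivalence to between 3.2% and 2.4%, and the four moderately Test-sided mixes examined stay between 3.9% and 4.8%. Inflation above 5% requires worsening concentrated in Test: above about 2.1% if Reference has none, reaching 7.1% at 5%. Both active arms receive ketoconazole 2%, so no worsening at all in Reference is an extreme case. All these figures rest on assumed worsening rates. If worsening withdrawals proved frequent and uneven between the active arms, the disposition table and the listings would show it.

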10.3.3 Restrictions During the Study

The following concomitant medications will not be allowed while enrolled in the study:

- Any topical products applied to the treatment area
- Any systemic (e.g., oral or injectable) antibiotics or anti-fungals
- Systemic corticosteroids or immunosuppressive drugs.
- Anti-pruritics, including antihistamines, within 24 hours of study visits.

Patients will be instructed not to use any occlusive wrappings or dressings over the treatment area during the study.

The use of hormonal contraceptives should not be initiated or changed during the study.

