10.6.3 Perform Pregnancy Test

All females of childbearing potential will have a urine pregnancy test performed at each visit. The test must be negative at Visit 1 for the patient to be eligible for inclusion in the study. If the patient is female and not considered of childbearing potential, then the reason must be documented in the patient's source documents.

Any patient who becomes pregnant during the study should be discontinued and end of study procedures (Visit 3 procedures) completed. The outcome of the pregnancy should be followed by the Investigator to the conclusion of the pregnancy. The pregnancy will be reported as an AE.

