10.6.5 Review and Assessment of Concomitant Medications

At Visit 1, patients will be questioned about medication use over the previous six months. At all subsequent visits, patients will be questioned about ongoing or new concomitant medication use.

CONFIDENTIAL PROTOCOL

A Randomized, Double-Blind, Vehicle-Controlled, Parallel-Design, Multiple-Site Clinical Study to Evaluate the Therapeutic Equivalence of Ketoconazole Cream 2% (Encube Ethicals Pvt Ltd) to Ketoconazole Cream 2% (G&W Laboratories Inc.) in the Treatment of Tinea Pedis

At Visit 2, any patient who has used medications restricted by the protocol may be discontinued from the study. If discontinued, all end of study procedures (Visit 3 procedures) should be performed.

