10.6.11 Collect Sample for Mycological Culture

If, at Visit 1, the patient meets all of the other inclusion/exclusion criteria, including a positive KOH wet mount test, then a sample will be sent to the centralized laboratory for fungal culture. As it could take up to 28 days or more for the results of the fungal cultures to be known, the Investigator can enroll patients into the study if they meet all of the other inclusion/exclusion criteria pending the results of the fungal culture. Culture must be positive for *T. rubrum*, *T. mentagrophytes* or *E. floccosum* for the patient to be included in the modified intent-to-treat (mITT) and per-protocol (PP) populations.

The sample for the culture should be placed into the transport kit provided by the central laboratory. The kit should be sealed according to the directions on the back of the kit itself. The sample kit should be sent to the central laboratory as instructed in the laboratory manual provided by ACM-Pivotal Global Central Laboratory.

ACM Pivotal Laboratory
[name]
[name]
[contact]

If the results of the baseline culture are positive, patients may continue in the study and samples for mycological culture will be obtained from the target lesion site at Visit 3. If the results of the baseline culture are negative, the patient should be discontinued and early termination procedures should be performed. No mycological culture sample should be collected as part of the early termination procedures.

Mycological culture samples will not be collected for patients with a positive KOH wet mount at Visit 3.

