12.2.4 Source Documents and Electronic Case Report Forms

All patients will be identified by initials, date of birth, and a unique patient number. Source documents will be used to record all study-related data. Source document entries will be used to complete eCRFs. A set of eCRFs will be completed for each patient randomized in the study. All data and eCRFs will be reviewed, evaluated, and signed by the Investigator.

The original source documents and a copy of the corresponding eCRFs will be retained by the Investigator. Patients who terminate early from the study will have the Visit 3 (end of study) source/eCRF completed.

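### Does it matter that the mITT rules do not say whether results taken at early termination count as the Day 56 outcome?

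*SAP*

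**What the plan says.** SAP section 6 defines the primary endpoint as Therapeutic Cure at the test-of-cure visit, two weeks after treatment ends (Day 56 ± 4). SAP section 7 states that mITT patients discontinued early for reasons other than lack of effect "will be excluded from the PP population and included in the mITT population using LOCF". That sentence does not name the visit to be carried forward. The next sentence does: a patient not discontinued for lack of effect who "does not have KOH or mycological culture results at Visit 3, this patient will be evaluated for the primary and secondary endpoints" with Visit 1 as the source. SAP sections 8.2.1 and 8.5 and Protocol section 11.3.2 repeat the rule.

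Exit data are recorded as follows:

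- Protocol 12.2.4: "Patients who terminate early from the study will have the Visit 3 (end of study) source/eCRF completed".
- Protocol 10.6.3: "Any patient who becomes pregnant during the study should be discontinued and end of study procedures (Visit 3 procedures) completed".
- Protocol 10.6.5: "At Visit 2, any patient who has used medications restricted by the protocol may be discontinued from the study", followed by "If discontinued, all end of study procedures (Visit 3 procedures) should be performed". The restricted list in Protocol 10.3.3 includes "Any systemic (e.g., oral or injectable) antibiotics or anti-fungals".
- Protocol 10.6.11, in the paragraph on negative baseline cultures: "No mycological culture sample should be collected as part of the early termination procedures".
- SAP shells T14.2.7.1 and T14.2.8.1 put Visit 3 and early termination on one row.

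The Day 52 to 60 window is a criterion for the PP population only.

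**The concern.** Take an mITT patient discontinued at Visit 2 over a restricted medication, whose exit KOH and culture are negative and whose scores are low.

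- **Reading A.** The exit record on the Visit 3 form is the Visit 3 result. The patient is a Therapeutic Cure, although there was no interval off treatment.
- **Reading B.** Visit 3 means Day 56 ± 4. The patient has no result then, Visit 1 is carried forward, and the patient fails, because mITT entry requires positive baseline KOH and culture and a baseline erythema score of at least 2.

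Two competent programmers could score this patient differently in the superiority test, which is one of the two conclusions the study must reach. Reading A would also report a result taken at the end of treatment as an off-treatment cure. The bias could go either way, depending on which arm's leavers test clear.

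**Working it through.** **1. Who is affected.** Several groups come out the same under either reading:

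- Lack-of-effect discontinuations have no mycology at exit and get no carry-forward.
- Patients with a negative baseline culture are not in mITT.
- Patients lost to follow-up have no exit tests and fail.
- Patients who leave before the baseline culture is known (Protocol 10.6.11: up to 28 days or more) would normally have no exit mycology and fail.

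That leaves mainly pregnancies and Visit 2 discontinuations over a restricted medication. Adverse-event and consent-withdrawal exits have the Visit 3 form completed, but no text expressly directs mycology for them. The PP analysis is not involved: apart from lack-of-effect failures, it needs a final visit in Day 52 to 60, and it uses no carry-forward.

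**2. The plan's own figure.** Inputs from SAP section 5: 216 per active arm, 108 placebo, Test 40%, Reference 45%, placebo 10%, two-sided 0.05, continuity-corrected Z-test with pooled standard error. For Test against placebo:

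- Pooled rate = (216 × 0.40 + 108 × 0.10)/324 = 0.30
- Null SE = √[0.30 × 0.70 × (1/216 + 1/108)] = 0.0540
- Alternative SE = √[0.40 × 0.60/216 + 0.10 × 0.90/108] = 0.0441
- Correction = 0.5 × (1/216 + 1/108) = 0.0069
- z = (0.30 − 0.0069 − 1.96 × 0.0540)/0.0441 = 4.25, so power is 0.99999

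Reference gives more than 0.99999. The stated figure of at least 99% is confirmed. (The site-stratified CMH test is approximated by this unstratified test, as the plan itself does.)

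**3. What cure rate to expect among leavers.** The documents give none directly. They do give PP rates of 45% and 50%, mITT rates of 40% and 45%, and 80% conversion from mITT to PP. Cure among mITT patients outside PP is therefore:

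- Test: (0.40 − 0.8 × 0.45)/0.2 = 20%
- Reference: (0.45 − 0.8 × 0.50)/0.2 = 25%

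This group also contains patients who did not leave early, so the rates are a guide only.

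**4. The two readings compared.** Assumptions not in the documents: a share *e* of mITT leaves early, half of them have exit mycology, placebo cure at exit is 10%, and those who stay have 40% (Test) and 10% (placebo). Test cure at exit is the 20% from step 3.

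- Reading B rates: (1 − *e*) × 0.40 and (1 − *e*) × 0.10
- Reading A adds *e* × 0.5 × 0.20 and *e* × 0.5 × 0.10
- Gap between readings in the Test-minus-placebo difference: *e* × 0.5 × (0.20 − 0.10)

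| Leave early | Reading B rates | Reading A rates | Gap (points) | Test patients changed, of 216 | Power B | Power A |
|---|---|---|---|---|---|---|
| 5% | 38.0 v 9.5 | 38.5 v 9.75 | 0.25 | 1.1 | 0.99997 | 0.99997 |
| 10% | 36.0 v 9.0 | 37.0 v 9.5 | 0.50 | 2.2 | 0.99991 | 0.99993 |
| 15% | 34.0 v 8.5 | 35.5 v 9.25 | 0.75 | 3.2 | 0.99978 | 0.99983 |

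On placebo, fewer than one patient of 108 changes in each row (at most 108 × 0.15 × 0.5 × 0.10 = 0.8). For Reference at 25%, the gap is *e* × 0.5 × 0.15, or about 0.4 to 1.1 points.

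**5. An upper bound from the plan's own rates.** Suppose all 20% of mITT patients outside PP are early leavers with exit mycology. Failing them all moves Test from 40% to 36% (0.04 × 216 = 8.6 patients), Reference from 45% to 40% (10.8 patients), and placebo from 10% to 8%. Power stays above 99.99% for both comparisons.

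**6. Stress cases under Reading A.** Let vehicle leavers clear more often than active leavers (40% against 10%). With half having mycology, power is 0.9999, 0.9994 and 0.9971 at 5%, 10% and 15% leaving. If all leavers have mycology it is 0.9998, 0.9973 and 0.982, and 0.927 at 20% leaving. Only if every placebo leaver is cured and no active leaver is does power fail badly: 0.995, 0.873 and 0.085 at 5%, 10% and 20%. Under Reading B it stays at 0.9995 even with 20% leaving.

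**The case for a change.** The strongest case for a change is that a primary outcome should be derivable from the text for every patient, and here it is not. The shared shell row for Visit 3 and early termination is a display convention and the Visit 3 form at exit is a recording convention; neither is an endpoint rule, and both sit uneasily with an endpoint defined at Day 56 ± 4. The disposition shell T14.1.1 even lists an early Visit 3 as a reason for termination, so off-window results are foreseen. A clarifying sentence would cost little.

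It stands that the text is silent, and that a sentence would be tidy. Three things limit its force.

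- The readings are not evenly balanced. The form, the name given to the exit procedures and the shell labels all point to counting exit results. Reading B rests on the Day 56 definition.
- The group is narrow. If the bar on exit culture in Protocol 10.6.11 is read as general rather than confined to negative-baseline patients, it is narrower still.
- The fuller remedies go beyond clarification. Failing all leavers on both secondary endpoints, setting a minimum number of days off treatment, or failing antifungal users who do have Day 56 results are choices of estimand, on which statisticians would differ. For a restricted-medication user who stays in and is tested at Day 56, the derivation has no gap: the observed result applies.

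**Conclusion.** No change follows. The SAP leaves a detail of derivation open, and an analyst can fill it sensibly either way, with the same rule in all arms. SAP section 4 keeps analysis staff blinded and releases the randomization schedule only after database lock, so the convention can be set blind. Listings L16.2.1 and L16.2.6.2 show discontinuation reasons, KOH and culture by visit, and the resulting classification, so a reader of the report can rescore the few patients concerned.

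On the plan's implied 20% cure among Test patients outside PP, with an assumed 10% on placebo, 5% to 15% leaving and half having exit mycology, the readings differ by 0.25 to 0.75 points of a planned 30, or about one to three Test patients of 216. Superiority power is above 99.9% under both, and PP equivalence does not depend on the point. The exit share, the share with mycology and cure at exit are assumptions. Power falls below 98% only under combinations such as 20% leaving, all with exit mycology, and vehicle leavers clearing four times as often as active leavers. Nothing in the documents suggests that.
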